7.2. Foreseeable Medical Occurrences

The foreseeable ARs following vaccination with pEVAC-PS include injection site pain, erythema, warmth, swelling and pruritus, myalgia, arthralgia, headache, fatigue, fever, feverishness, malaise and nausea. These adverse events will be listed as solicited adverse

events providing they occur within 7 days following the day of vaccination. AEs other than these, or those AEs occurring outside of the 7 days after vaccination, will be listed as unsolicited adverse events.

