1.4 Pre-clinical studies of pEVAC-PS

1.5. Dose Rationale

The CE-marked PharmaJet Tropis intradermal (ID) delivery of DNA has demonstrated to be highly effective at reducing the dose required for anti-viral responses in several different systems. An adaptive dose escalation regime follows to discover the lowest dose of DNA which will produce an effective immune response when delivered intradermally, with potential doses of 1.2mg, 0.8mg, 0.4mg and 0.2mg.

Objective	Outcome measure			
Primary To assess the safety and reactogenicity of a new pan-Sarbeco Coronavirus DNA candidate vaccine pEVAC-PS in a boosting regime in healthy volunteers.	 a) Occurrence of solicited local reactogenicity signs and symptoms for 7 days following vaccination; b) Occurrence of solicited systemic reactogenicity signs and symptoms for 7 days following vaccination; c) Occurrence of unsolicited adverse events (AEs) for 28 days following vaccination; d) Change from baseline for safety laboratory measures and; e) Occurrence of disease enhancement episodes 			
Secondary To assess the humoral immunogenicity of pEVAC-PS when administered to healthy volunteers as a booster vaccine, through the analysis of SARS-CoV and SARS-CoV-2 RBD antibody titres. To assess the humoral immunogenicity of the candidate vaccine pEVAC-PS at 28 days (4 weeks) after 2 doses of pEVAC-PS have been administered 28 days apart, given by needle-free technology (PharmaJet); both administered in split doses, left and right deltoids (when >0.2mg)	 a) Serology: receptor binding domain (RBD) responses in the majority of vaccinees per group for SARS-CoV and SARS-CoV-2 			
Secondary Assess optimum dosing of candidate vaccine pEVAC-PS	a) Compare dose tolerability and results of immunogenicity of up to four different doses of PharmaJet ID			

2. Objectives and Endpoints

	administration at 28 days (4 weeks)
	after the second dose of vaccine
Secondary	a) Serology: receptor binding domain
To assess long term (up to 12 months)	(RBD) for SARS-CoV and SARS-
humoral immunogenicity of the candidate	CoV-2 RBD pre and post-
vaccine pEVAC-PS administered by the	immunisation.
needle-free technology (PharmaJet)	
administered as 2 doses (split L&R	
when >0.2mg)	

3. Study Design

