5.3.9. Distribution, review and completion of diary cards

Volunteers will be asked to complete a diary card for a period of 2 months following administration of vaccine on Day 0. A separate diary will be issued for each 28 day period post vaccination. An oral thermometer, tape measure and access to a paper diary card for solicited and unsolicited AEs will be given to each volunteer. The diaries will collect information on the timing and severity of the following solicited AEs:

Local solicited AEs	Systemic solicited AEs
Pain	Fever
Redness	Feverishness
Warmth	Joint pains
ltch	Muscle pains
	Fatigue
	Headache
	Nausea
	Malaise

Table 4: Solicited AEs as collected on post vaccination diary cards

Volunteers will be instructed on how to self-assess the severity of these AEs. There will also be space on the diary card to self-document unsolicited AEs, and whether medication was taken to relieve the symptoms.

Volunteers will be asked to bring their diary to the study site at each follow up visit. Diaries will be reviewed by a member of the study team. All diaries will be collected at the Week 8 follow up visit.

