7.5.2 Assessment of Severity

The severity of clinical and laboratory adverse events will be assessed according to the scales in **Tables 7-10**.

Adverse Event	Grade	Intensity
Pain at injection site	1	Pain that is easily tolerated
	2	Pain that interferes with daily activity
	3	Pain that prevents daily activity
Erythema at injection site*	1	>3 - ≤ 50mm
	2	>50 - ≤100mm
	3	>100mm
Swelling at injection site*	1	>3 - ≤ 20mm
	2	>20 - ≤ 50mm
	3	>50mm
Itching at injection site	1	Itching that is easily tolerated
	2	Itching that interferes with daily activity
	3	Itching that prevents daily activity

* erythema or swelling ≤3mm is an expected consequence of skin puncture and will therefore not be considered an adverse event

Table 8:	Severity	grading	for p	hysical	observations

Adverse Event	Grade 1 (mild)	Grade 3 (severe)			
Fever (oral)	37.6°C - 38°C 38.1°C - 39°C		>39°C		
Tachycardia (bpm)*	101-115	101-115 116-130			
Bradycardia (bpm)**	50-54	40-49	<40		
Systolic Hypertension (mmHg)	141-159 160-179		≥180		
Diastolic Hypertension (mmHg)	91-99	100-109	≥110		
Systolic Hypotension (mmHg)***	85-89	80-84	<80		

*Taken after ≥10 minutes at rest

** When resting heart rate is between 60-100 beats per minute. Use clinical judgement when characterising bradycardia among some healthy subjection populations, for example, conditioned athletes.

*** Only if symptomatic (e.g. dizzy / light headed)

Table 9: Severity grading criteria for local and systemic AEs

Grade	Criteria
GRADE 0	None; Symptom not experienced
GRADE 1	Mild: Short-lived or mild symptoms; medication may be required. No limitation to usual activity
GRADE 2	Moderate: Mild to moderate limitation in activity. Medication may be required
GRADE 3	Severe: Considerable limitation in activity. Medication or medical attention required

Routine Haematology		Lab Range	Grade 0	Grade 1	Grade 2	Grade 3	
	Male		130 - 170	126 - 170	115 - 125	100 - 114	<100
Haemoglobin	Female	g/i	120 - 150	114 - 150	103 - 113	90 - 104	<90
White blood	Elevated				11.50 - 15.00	15.01 - 20.00	>20
cells	Low	x10 ⁹ /I	4.00 - 11.00	3.51 - 11.49	2.50 - 3.50	1.50 - 2.49	<1.50
Platelets		x10 ⁹ /l	150 - 400	136 - 400	125 - 135	100 - 124	<100
Neutrophils		x10 ⁹ /l	2.0 - 7.5	1.5 - 7.5	1.00 - 1.49	0.50 - 0.99	<0.50
Lymphocytes		x10 ⁹ /I	1.5 - 4.0	1.0 - 4.0	0.75 - 0.99	0.50 - 0.74	<0.50
Eosinophils		x10 ⁹ /l	0.0 - 0.5	0.0 - 0.64	0.65 - 1.50	1.51 - 5.00	>5.00
Routine Biochemistry			Lab Range	Grade 0	Grade 1	Grade 2	Grade 3

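### Injection-site swelling is declared a solicited reaction and graded in millimetres, but the diary list omits it, so this component of primary outcome (a) is not prompted for and is probably under-counted, most clearly after dose 2

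*Protocol*

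**What the plan says.** Four places in the protocol bear on this.

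- **Endpoint.** Primary outcome (a) in section 2 is "Occurrence of solicited local reactogenicity signs and symptoms for 7 days following vaccination".
- **Which events are solicited.** Section 7.2 gives the foreseeable reactions, which "include injection site pain, erythema, warmth, swelling and pruritus", followed by eight systemic terms. It then says: "These adverse events will be listed as solicited adverse" events if they occur within 7 days of the vaccination day. For everything else: "AEs other than these, or those AEs occurring outside of the 7 days after vaccination, will be listed as unsolicited adverse events".
- **What the diary asks.** Section 5.3.9 says: "The diaries will collect information on the timing and severity of the following solicited AEs". The list that follows is captioned "Table 4: Solicited AEs as collected on post vaccination diary cards". Its local column holds pain, redness, warmth and itch. The section adds: "There will also be space on the diary card to self-document unsolicited AEs".
- **How swelling is graded.** The injection-site table in section 7.5.2 has a row for "Swelling at injection site": grade 1 is above 3 mm up to 20 mm, grade 2 above 20 mm up to 50 mm, grade 3 above 50 mm. Swelling of 3 mm or less is not an adverse event.

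**The concern.** A solicited event is one that every participant is asked about on every day of the window, so that no entry can be read as no event. Section 7.2 and the grading table treat swelling in this way. A diary built from Table 4 would not. A swelling rate reported as solicited would then mix staff observation, general questioning and volunteered comments, and a blank could mean either no swelling or no question.

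The classification also becomes ambiguous. Swelling on day 2 is solicited under section 7.2, but the only place on the card for a volunteer to write it is the space for unsolicited events. That matters beyond labelling, because section 7.5.1 asks for a causality assessment of every unsolicited event.

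Local reactogenicity is part of the primary objective of this first-in-human study. Table 5 shows 1, 2, 4 and 6 intradermal injections per visit at 0.2, 0.4, 0.8 and 1.2 mg, so local reactions are a natural point of comparison between doses.

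**Working it through.** The protocol gives no figure to reproduce. The check is a comparison of lists and of the visit schedule.

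**1. Terms in section 7.2 against Table 4**

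| Section 7.2 | Table 4 (diary) |
|---|---|
| Injection-site pain | Pain |
| Erythema | Redness |
| Warmth | Warmth |
| Swelling | none |
| Pruritus | Itch |
| Myalgia | Muscle pains |
| Arthralgia | Joint pains |
| Headache | Headache |
| Fatigue | Fatigue |
| Fever | Fever |
| Feverishness | Feverishness |
| Malaise | Malaise |
| Nausea | Nausea |

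Local terms: 5 in section 7.2 and 4 in Table 4. Systemic terms: 8 and 8. Of 5 + 8 = 13 terms, 12 match and swelling alone does not. That pattern looks like an omission, not a decision to leave swelling out.

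**2. Is swelling meant to be measured?** Yes. The scale in section 7.5.2 needs a diameter, and section 5.3.9 issues a tape measure. Table 4 has no line on which to record the result.

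**3. Other scheduled chances to record swelling within 7 days (Table 2 and sections 5.3.8, 5.5.1, 5.5.2)**

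| | After dose 1 (Day 0) | After dose 2 (Day 28) |
|---|---|---|
| Site inspection at 30 minutes | yes | yes |
| Next-day telephone call | Day 1 | not in Table 2; section 5.5.1 can be read as including it |
| Clinic visits within 7 days | Day 3, Day 7 | none |
| Next tabulated attendance | Day 3 | Day 42 |

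The nominal gap after dose 2 is 42 − 28 = 14 days, twice the 7-day window. Visit windows count from enrolment: ±7 days at Day 28 and ±3 days at Day 42. The gap is therefore 14 + b − a days, where a is the shift of dose 2 and b the shift of the Day 42 visit. It falls to 7 days or fewer only if a − b is at least 7, for example dose 2 given on Day 35 (a = 7) with the visit on time (b = 0). With dose 2 on schedule the shortest gap is 14 − 3 = 11 days.

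Section 3.1 mentions a review of group 2a at 72 hours after the second dose, but Table 2 has no matching attendance. For the 7 days after dose 2 the diary is thus the main scheduled source.

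**4. Direction and size.** Unprompted reporting would be expected to miss events, so the likely direction is an under-count, more so after dose 2. The protocol gives neither an expected swelling rate nor a capture rate for unprompted reports, so the size cannot be derived from it.

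**The case against.** The strongest reply is that swelling is far from invisible. Staff inspect the site at 30 minutes after each vaccination. After dose 1 they see the participant on Days 3 and 7. Section 5.5.2 has them assess new or undocumented symptoms at visits, and section 7.6.1 records every adverse event seen or reported within 28 days. This stands. A reader might infer that swelling reaches the data only as free text, or that it can never be graded; the protocol does not support either reading, least of all after dose 1. The reply is weak after dose 2, where a visit nominally 14 days later can ask about swelling that has gone but cannot measure it.

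Second, the effect on outcome (a) is narrow. The other four local terms are prompted, so the proportion with any local reaction changes only for a participant who has swelling and none of the four. This also stands for that summary. It does not protect the rate for swelling itself. Nor does it protect the worst local grade, since the swelling cut-offs (20 and 50 mm) are lower than those for erythema (50 and 100 mm). The analysis is descriptive, so no error rate or power is involved.

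Third, a reader might infer that the gap distorts the choice between doses. The protocol does not support a direct link. The expansion rule in section 3.1.1 uses responder counts, and takes the lower dose if groups 2a and 2b both have 9 responders. Reactogenicity enters only qualitatively, in sections 3.1, 3.3 and 8.1. The group holding rules in section 7.9.1 concern serious events. The omission applies at every dose, and no differential bias between doses is shown.

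Finally, the diary card itself is not in the protocol, and a row could have been lost when Table 4 was read from PDF. Nothing in the table suggests a break, so this is only a residual caution.

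**Conclusion.** The inconsistency is real: section 7.2 and the grading table treat swelling as a solicited, measured event, and Table 4 does not collect it. One of five declared local components of primary outcome (a) would not be prompted for. Its rate would probably be under-counted, particularly after dose 2, and the same event could be filed as solicited or unsolicited.

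No percentage or participant count can be attached to the under-count from the document, and none is claimed. Sample size, power and error rates are unaffected, and any influence on dose selection is indirect. The conclusion assumes that the diary follows Table 4 as printed and that participants report less when not asked. It is worth correcting before dosing, because daily measurements that were never requested cannot be recovered by any later analysis plan.

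**What to change.** Reconcile section 7.2, Table 4 and the injection-site grading table so that the same local terms are solicited, graded and analysed. The direct way is to add swelling (mm) to the local column of Table 4, to both 28-day diary cards and to the eCRF, measured with the tape measure already issued under section 5.3.9.

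Removing swelling from the solicited list in section 7.2 would also make the two lists agree. It would, however, take swelling out of primary outcome (a) and leave a millimetre scale with no planned daily measurement to feed it.

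The cost is one extra diary line and one eCRF field, with no added visit. Reported local reactogenicity may come out slightly higher.

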7.3 Expected Serious Adverse Events

There are no expected serious adverse events for this study.

7.4. Adverse Events of Special Interest

Adverse events of special interest will be reported as SAEs. These are:

- Severe hypersensitivity reactions (e.g. Anaphylaxis)
- Any new, suspected auto-immune disease
- Myocarditis or pericarditis
- Blood clotting events associated with low platelets (thrombocytopaenic thrombosis)
- COVID-19 disease or SARS-CoV-2 infection

7.5. Evaluation of AEs, SAEs and other safety events

When an AE/SAE occurs, the investigator is responsible for reviewing all documentation related to the event. The investigator will record all relevant information on the eCRF and make an assessment on causality and severity.

7.5.1. Assessment of Causality

For every unsolicited AE, an assessment of the relationship of the event to the administration of the vaccine will be undertaken by the CI or the CI-delegated clinician at the site. An intervention-related AE refers to an AE for which there is a probable or definite relationship to administration of a vaccine. An interpretation of the causal relationship of the intervention to the AE in question will be made, based on the type of event; the relationship of the event to the time of vaccine administration; and the known biology of the vaccine therapy (Table 6). Causality assessment will take place during planned safety reviews, interim analyses (e.g. if a holding or stopping rule is activated) and at the final safety analysis, except for SAEs, for which causality should be assigned by the reporting Investigator.

0	No Relationship	Alternate aetiology (clinical state, environmental or other interventions); and Does not follow known pattern of response to study product
1	Unlikely	Unlikely temporal relationship to study product and Alternate aetiology likely (clinical state, environmental or other interventions) and Does not follow known typical or plausible pattern of response to study product.
2	Possible	Reasonable temporal relationship to study product; or Event not readily produced by clinical state, environmental or other interventions; or Similar pattern of response to that seen with other vaccines
3	Probable	Reasonable temporal relationship to study product; and

Table 6: Guidelines for assessing the relationship of vaccine administration to an AE.

		Event not readily produced by clinical state, environment, or other interventions or Known pattern of response seen with other vaccines
4	Definite	Reasonable temporal relationship to study product; and Event not readily produced by clinical state, environment, or other interventions; and Known pattern of response seen with other vaccines

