7.1. Safety definitions

Adverse Event (AE)

An AE is any untoward medical occurrence in a volunteer, including a dosing error, which may occur during or after administration of the vaccine and does not necessarily have a causal relationship with the intervention. An AE can therefore be any unfavourable and unintended sign (including an abnormal laboratory finding), symptom or disease temporally associated with the study intervention, whether or not considered related to the study intervention.

Adverse Reaction (AR)

An AR is any untoward or unintended response to the vaccine. This means that a causal relationship between the inoculum and an AE is at least a reasonable possibility, i.e., the relationship cannot be ruled out. All cases judged by either the reporting medical investigator or the sponsors as having a reasonable suspected causal relationship to the inoculum (i.e. possibly, probably or definitely related to the inoculum) will qualify as adverse reactions.

Unexpected Adverse Reaction (UAR)

An adverse reaction, the nature or severity of which is not consistent with the applicable information about the vaccine in the protocol, is considered as an unexpected adverse reaction.

Serious Adverse Event (SAE)

An SAE is an AE that results in any of the following outcomes, whether or not considered related to the study intervention.

- Death (i.e., results in death from any cause at any time)
- Life-threatening event (i.e., the volunteer was, in the view of the investigator, at immediate risk of death from the event that occurred). This does not include an AE that, if it occurred in a more serious form, might have caused death.
- Persistent or significant disability or incapacity (i.e. substantial disruption of one's ability to carry out normal life functions).
- Hospitalisation other than admission in the NIHR-CRF, regardless of length of stay, even if it is a precautionary measure for continued observation. Hospitalisation (including inpatient or outpatient hospitalisation for an elective procedure) for a pre-existing condition that has not worsened unexpectedly does not constitute a serious AE.

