- An important medical event (that may not cause death, be life threatening, or require hospitalisation) that may, based upon appropriate medical judgment, jeopardise the volunteer and/or require medical or surgical intervention to prevent one of the outcomes listed above. Examples of such medical events include allergic reaction requiring intensive treatment in an emergency room or clinic, blood dyscrasias, or convulsions that do not result in inpatient hospitalisation.
- Congenital anomaly or birth defect.

Serious Adverse Reaction (SAR)

An adverse event that is both serious and, in the opinion of the reporting investigator or sponsor, believed to be possibly, probably or definitely due to the inoculum or any other study treatments, based on the information provided in the protocol.

Suspected Unexpected Serious Adverse Reactions (SUSARs)

A SUSAR is a SAE that thought to be possibly, probably or definitely related to the inoculum and is unexpected in nature (when assessed against the IB).

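### Section 7.5.1 leaves Possible events out of its definition of an intervention-related AE, which contradicts section 7.1 and the threshold used elsewhere in the safety section

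*Protocol*

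**What the plan says.** Protocol section 7.5.1 has each unsolicited AE scored for its relationship to the vaccine on the five-point scale of Table 6: 0 No Relationship, 1 Unlikely, 2 Possible, 3 Probable, 4 Definite. The table is captioned "Guidelines for assessing the relationship of vaccine administration to an AE". The section then fixes what counts as related: "An intervention-related AE refers to an AE for which there is a probable or definite relationship to administration of a vaccine". Scoring takes place at planned safety reviews, at interim analyses and "at the final safety analysis, except for SAEs, for which causality should be assigned by the reporting Investigator".

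Section 7.1 draws the line one step lower in three definitions:

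- Adverse reaction: events judged by the investigator or the sponsor to be "possibly, probably or definitely related to the inoculum) will qualify as adverse reactions".
- Serious adverse reaction: an event "believed to be possibly, probably or definitely due to the inoculum or any other study treatments".
- SUSAR: "A SUSAR is a SAE that thought to be possibly, probably or definitely related to the inoculum", and unexpected.

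LSC notice in 7.6.2, the group holding rules in 7.9.1, the individual stopping rule in 7.9.2 and the LSC review list in 7.10 all take in possibly related serious events. Section 7.10 also gives the LSC power to hold the study after an intervention-related SAE, and that sentence states no threshold of its own.

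**The concern.** The protocol gives two answers to whether an event scored Possible is related to the vaccine. The narrower answer sits in the section that governs causality scoring, so it is the one a programmer or safety reviewer would naturally apply when building a table of related events. That table would leave out events that 7.1 classes as adverse reactions.

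This could matter because 8.1 bases dose adaptation on all available tolerability and immunogenicity information, and a secondary outcome in section 2 compares dose tolerability. With 6 to 21 participants at a dose, reclassifying one or two people visibly changes a percentage. Two readers could report different vaccine-related rates for the same dose without either departing from the protocol.

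**Working it through.** **Step 1. Thresholds side by side, on the Table 6 scale.**

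| Section | Use | Scores counted |
|---|---|---|
| 7.5.1 | Intervention-related AE | 3, 4 |
| 7.1 | Adverse reaction, SAR, SUSAR | 2, 3, 4 |
| 7.6.2 | LSC notice of SAEs within 24 hours | 2, 3, 4 |
| 7.9.1, 7.9.2 | Group holding, individual stopping | 2, 3, 4 |
| 7.10 | LSC review of SAEs | 2, 3, 4 |
| 8.2 | Tabulation of observed AEs | no relatedness filter |

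Only 7.5.1 leaves out score 2.

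**Step 2. How easily an event lands on score 2.** Row 2 of Table 6 joins its conditions with *or*: "Reasonable temporal relationship to study product; or Event not readily produced by clinical state, environmental or other interventions; or Similar pattern of response". Read literally, reasonable timing alone is enough. Score 3 needs reasonable timing and a further condition. Score 2 is therefore a natural place for an unsolicited AE soon after a dose with nothing else to implicate the vaccine, so the disputed category need not be rare.

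**Step 3. Size of the discrepancy.** For a group of n, each participant whose highest-scored unsolicited AE is Possible counts under 7.1 and not under 7.5.1. The shift per such participant is 100/n percentage points. Group sizes come from 3.3, and the 21 at a selected dose (9 + 12) from 8.1.

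- n = 6 (Group 1): 100/6 = 16.7
- n = 9 (Group 2a or 2b): 100/9 = 11.1
- n = 12 (expanded Group 1, Group 2c or Group 3): 100/12 = 8.3
- n = 21 (selected dose): 100/21 = 4.8

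Illustration with an assumed count: if 3 of 6 participants have Possible as their highest score, 7.1 gives 3/6 = 50% (exact 95% interval 11.8 to 88.2%) and 7.5.1 gives 0/6 = 0% (0 to 45.9%).

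**Step 4. What depends on the 7.5.1 wording.** The outcomes in section 2 are occurrences and changes from baseline, with no causality condition. Section 8.2 tabulates observed AEs. The triggers in 7.6.2, 7.9.1 and 7.9.2 state their own threshold and can be followed as written. That leaves two places: any summary of vaccine-related unsolicited AEs, and the unqualified phrase in 7.10.

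**Step 5. SARS-CoV-2 infection.** Section 7.4 lists it as an event of special interest reported as an SAE, and disease enhancement is primary outcome (e). Under 7.6.2 every SAE reaches the chief investigator (or a delegate) and the sponsor within 24 hours. The LSC must be told within 24 hours only from score 2 upward. An infection soon after a dose can fit row 0 (an alternate aetiology, and "Does not follow known pattern of response to study product") as well as row 2 on timing. The COVID-19 pathway in 5.5.3 has no LSC step.

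The protocol gives no infection rate. At an assumed 0.1% to 1% per person-week:

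- 36 participants × 26 weeks = 936 person-weeks, giving 0.9 to 9.4 infections.
- With the final 12 followed to Day 365, 24 × 26 + 12 × 52 = 1248 person-weeks, giving 1.2 to 12.5.

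These figures use the 36-person maximum and count infections, not enhancement episodes.

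**The case against.** The strongest reply is that the narrow definition changes nothing that the protocol plans. No outcome in section 2 and no analysis in 8.2 specifies a related-AE rate. Causality scoring in 7.5.1 is for unsolicited AEs, whereas tolerability is also measured by solicited reactions and laboratory changes, which carry no causality filter. Whether a statistical analysis plan contains a related-AE table cannot be seen. This stands, and it limits the point to a possible summary rather than a specified estimate. It does not remove the contradiction, because 7.5.1 itself places causality assessment at the safety reviews and the final safety analysis.

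A reader might infer that a Possible SAE could escape a hold or LSC review. The documents do not support that. The notice and holding rules state their own threshold, the 7.10 review list includes possibly related SAEs shortly before the unqualified phrase, and 7.9.2 and 7.10 allow a hold on LSC advice for any single event.

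A reader might also infer that one investigator's score alone decides whether the LSC hears of an infection. It does not. Under 7.1 the sponsor may also judge an event related, the sponsor hears of every SAE within 24 hours, and 7.11 has the investigators review SAEs as they arise.

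Nor is LSC notice limited to possibly related SAEs an error. It is a consistent choice in 7.6.2 and 7.10. The LSC also receives AE data before interim safety analyses (7.6.1), monitoring reports are open to its review (10.1), and its chair may be consulted at any time. What remains is that none of these is a mandatory 24-hour route for an infection scored 0 or 1.

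**Conclusion.** The contradiction is real and the point is minor. Section 7.5.1 excludes Possible events from intervention-related AEs, while 7.1 and every stated safety threshold include them. A summary of vaccine-related unsolicited AEs could differ by 4.8 to 16.7 percentage points per affected participant, depending on group size. That shift needs no assumption. How many participants would be affected is unknown, and the 3 of 6 case is only an illustration.

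No primary outcome estimate, holding rule or LSC notification trigger is altered. The infection route is not an error in the plan. Faster LSC notice is worth considering only because infection is an event of special interest and disease enhancement is a primary outcome.

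**What to change.** In 7.5.1, replace *probable or definite* with *possible, probable or definite*. This aligns the definition with 7.1 and settles the 7.10 phrase. It costs one word and no data, visits or participants.

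Optional safety addition: state in 7.6.2 and 7.10 that every COVID-19 disease or SARS-CoV-2 infection is notified to the LSC within 24 hours regardless of causality score. The cost is a few extra notices, mostly for ordinary infections. At the assumed rates the totals in step 5 are an upper limit, because infections scored 2 or more are already notified and the trial may stop short of 36 participants. Table 6 and the rules in 7.9 can stay as they are.
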